The effect of fed/fasting state on PK and bioavailability of CVN766 will be analyzed. The analysis will be descriptively. In addition, a random effects mixed model on the log-transformed pharmacokinetic parameters (AUC_t , AUC_{inf} , AUC_{24} , and C_{max}) will be applied to explore the effect of food, where meal status (fed vs. fasted) will be included as a fixed effect and participant will be included as a random effect. The geometric mean for fed/fasted and their 90% CIs will be estimated from the model based on the least squares means. The ratio of the geometric means (geometric mean ratio) and its 90% CI of the

fed data compared to the fasted data will be obtained based on the exponential of the difference of least-squares means (LSM) from the model.

- Gender Effect

The effect of gender (male vs. female) on Dose Normalized PK parameters of CVN766 will be analyzed. A random effects mixed model on the log-transformed pharmacokinetic parameters:

SAD: C_{\max}/Dose , AUC_{24}/Dose , AUC_t/Dose , $AUC_{\text{inf}}/\text{Dose}$ and $t_{1/2z}$

MAD Day 1: AUC_{24}/Dose , C_{\max}/Dose , AUC_t/Dose , $t_{1/2z}$ and t_{\max} .

MAD Day 7: $C_{\max,ss}/\text{Dose}$, $AUC_{\text{tau}}/\text{Dose}$, AUC_t/Dose , $t_{1/2z}$ and t_{\max} .

will be applied to explore the effect of gender, where gender (male vs. female) will be included as a fixed effect and participant will be included as a random effect. The geometric mean for Male/Female and their 90% CIs will be estimated from the model based on the least squares means. The ratio of the geometric means (geometric mean ratio) and its 90% CI of the Male data compared to the Female data will be obtained based on the exponential of the difference of least-squares means (LSM) from the model.

Point estimates and 90% CIs for differences on the log scale will be exponentiated to obtain estimates for the ratios of geometric means and respective 90% CIs on the original scale.

For $t_{1/2z}$, a non-parametric analysis (Hodges-Lehmann estimate) will be used to produce the median difference between female and male. A p-value will be generated by the Wilcoxon signed-rank test.

3.4 Multiple Comparisons and Multiplicity Adjustments.

Not applicable for this study.

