Geometric LS Mean (90% CI)	xx.xx (xx.xx, xx.xx)	xx.xx (xx.xx, xx.xx)
Ratio of Geometric LS Means (Fed/Fasting)		xx.xx
90% CI for Ratio of Geometric LS Means (Fed/Fasting)		(xx.xx, xx.xx)

Source: Listing 16.2.6.3.1

LS = Least Square, SE = Standard Error, CI = Confidence Interval.

Programming Note:

- ANOVA model will be used
 - Fixed Effect: food status (fed, fasted)

Sponsor: Cerevance Gamma, Inc.
Protocol: CVN766-101

Data Cut-Off: 2022-10-26

- Random Effect: Subject

Table 14.2.8.1 Gender Effect Assessment of Plasma CVN766 Dose Normalized Pharmacokinetic Parameters SAD (Pharmacokinetic Population)

Analyte:xxxx
 Visit: Day 1

Treatment	Parameter	Statistics	Gender	
			Male	Female
Pooled CVN766	AUC24/Dose	n	xx	xx
		Geometric LS mean (90% CI)	xx.xx (xx.xx, xx.xx)	xx.xx (xx.xx, xx.xx)
		Geometric mean ratio(90% CI) (female vs male)		xx.xx (xx.xx, xx.xx)
	Cmax/Dose	n	xx	xx
		Geometric LS mean (90% CI)	xx.xx (xx.xx, xx.xx)	xx.xx (xx.xx, xx.xx)
		Geometric mean ratio(90% CI) (female vs male)		xx.xx (xx.xx, xx.xx)
	AUCt/Dose	n	xx	xx
		Geometric LS mean (90% CI)	xx.xx (xx.xx, xx.xx)	xx.xx (xx.xx, xx.xx)
		Geometric mean ratio(90% CI) (female vs male)		xx.xx (xx.xx, xx.xx)
	AUCinf/Dose	n	xx	xx
		Geometric LS mean (90% CI)	xx.xx (xx.xx, xx.xx)	xx.xx (xx.xx, xx.xx)
		Geometric mean ratio(90% CI) (female vs male)		xx.xx (xx.xx, xx.xx)
	Tl/2z	n	xx	xx
		Geometric LS mean (90% CI)	xx.xx (xx.xx, xx.xx)	xx.xx (xx.xx, xx.xx)
		Geometric mean ratio(90% CI) (female vs male)		xx.xx (xx.xx, xx.xx)
	Tmax	n	xx	xx
		Hodges-Lehmann estimate (Median)	xx.xx	xx.xx
		Hodges-Lehmann CI		xx.xx (xx.xx, xx.xx)

Source: Listing 16.2.6.3.1
 LS = Least Square, SE = Standard Error, CI = Confidence Interval.

Programming Note:

- ANOVA model will be used
 - Fixed Effect: Gender (Male, Female)
 - Random Effect: Subject

Programming Note:
 Include only the following cohorts;
 CVN766 5 mg, CVN766 15 mg, CVN766 45 mg(Fasted), CVN766 125 mg, CVN766 250 mg

Table 14.2.8.2 Gender Effect Assessment of Plasma CVN766 Pharmacokinetic Parameters MAD (Pharmacokinetic Population)

Analyte:xxxx
 Day 1

Treatment	Parameter	Statistics	Gender	
			Male	Female
Pooled CVN766	AUC24/Dose	n	xx	xx
		Geometric LS mean (90% CI)	xx.xx (xx.xx, xx.xx)	xx.xx (xx.xx, xx.xx)
		Geometric mean ratio(90% CI) (female vs male)		xx.xx (xx.xx, xx.xx)
	Cmax/Dose	n	xx	xx
		Geometric LS mean (90% CI)	xx.xx (xx.xx, xx.xx)	xx.xx (xx.xx, xx.xx)
		Geometric mean ratio(90% CI) (female vs male)		xx.xx (xx.xx, xx.xx)
	AUCt/Dose	n	xx	xx

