		Geometric LS mean (90% CI)	xx.xx (xx.xx, xx.xx)	xx.xx (xx.xx, xx.xx)
		Geometric mean ratio(90% CI) (female vs male)		xx.xx (xx.xx, xx.xx)
	Tl/2z	n	xx	xx
		Geometric LS mean (90% CI)	xx.xx (xx.xx, xx.xx)	xx.xx (xx.xx, xx.xx)
		Geometric mean ratio(90% CI) (female vs male)		xx.xx (xx.xx, xx.xx)
	Tmax	n	xx	xx
		Hodges-Lehmann estimate (Median)	xx.xx	xx.xx
		Hodges-Lehmann CI		xx.xx (xx.xx, xx.xx)

Analyte:xxxx
 Day 7

Treatment	Parameter	Statistics	Gender	
			Male	Treatment
	Cmax,ss/Dose	n	xx	xx
		Geometric LS mean (90% CI)	xx.xx (xx.xx, xx.xx)	xx.xx (xx.xx, xx.xx)
		Geometric mean ratio(90% CI) (female vs male)		xx.xx (xx.xx, xx.xx)
	AUCtau/Dose	n	xx	xx
		Geometric LS mean (90% CI)	xx.xx (xx.xx, xx.xx)	xx.xx (xx.xx, xx.xx)
		Geometric mean ratio(90% CI) (female vs male)		xx.xx (xx.xx, xx.xx)
	AUCt/Dose	n	xx	xx
		Geometric LS mean (90% CI)	xx.xx (xx.xx, xx.xx)	xx.xx (xx.xx, xx.xx)
		Geometric mean ratio(90% CI) (female vs male)		xx.xx (xx.xx, xx.xx)
	Tl/2z	n	xx	xx
		Geometric LS mean (90% CI)	xx.xx (xx.xx, xx.xx)	xx.xx (xx.xx, xx.xx)
		Geometric mean ratio(90% CI) (female vs male)		xx.xx (xx.xx, xx.xx)
	Tmax	n	xx	xx

Sponsor: Cerevance Gamma, Inc.
Protocol: CVN766-101

Data Cut-Off: 2022-10-26

Hodges-Lehmann estimate
(Median)

xx.xx

xx.xx

Source: Listing 16.2.6.3.2

LS = Least Square, SE = Standard Error, CI = Confidence Interval.

Programming Note:

- ANOVA model will be used
 - Fixed Effect: Gender (Male, Female)
 - Random Effect: Subject

Table 14.3.1.1 Summary of Concomitant Medications SAD (Safety Population)

Anatomical Therapeutic Class (ATC) [Level 3] Preferred Term (PT)	CVN766 5 mg (N=xx) n (%) m	etc.	Overall (N=xx) n (%) m
Subjects with at least one Concomitant Medication	xx (xx.x%) x	xx (xx.x%) x	xx (xx.x%) x
ATC 3	xx (xx.x%) x	xx (xx.x%) x	xx (xx.x%) x
PT 1	xx (xx.x%) x	xx (xx.x%) x	xx (xx.x%) x
PT 2	xx (xx.x%) x	xx (xx.x%) x	xx (xx.x%) x
...	xx (xx.x%) x	xx (xx.x%) x	xx (xx.x%) x
ATC 3	xx (xx.x%) x	xx (xx.x%) x	xx (xx.x%) x
PT 1	xx (xx.x%) x	xx (xx.x%) x	xx (xx.x%) x
PT 2	xx (xx.x%) x	xx (xx.x%) x	xx (xx.x%) x
.....			

Source: Listing 16.2.10.2.1

Concomitant medications are defined as any medication (other than the study drug) that was used at least once after the first administration of the study drug.

ATC class and preferred names within ATC class are presented in alphabetical order.

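### SAP 3.3 names a paired test for the male-female comparison, gives t1/2z and Tmax conflicting methods, and defines the sex ratio in the opposite direction to the table shells

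*SAP*

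**What the plan says.** SAP Section 3.3, Gender Effect, plans a mixed model on log-transformed PK parameters in which "gender (male vs. female) will be included as a fixed effect and participant will be included as a random effect". The parameters listed for that model include t1/2z for SAD, MAD Day 1 and MAD Day 7, and tmax for both MAD days. The ratio of geometric means and "its 90% CI of the Male data compared to the Female data will be obtained" from the exponentiated difference of LS means.

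For t1/2z the section then adds a second analysis: "a non-parametric analysis (Hodges-Lehmann estimate) will be used to produce the median difference between female and male", followed by "A p-value will be generated by the Wilcoxon signed-rank test".

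The list of inferential analyses at the end of Section 10.7 refers back to 3.3 for method. It includes Tmax for SAD, which the SAD list in 3.3 does not.

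In mock Tables 14.2.8.1 (SAD) and 14.2.8.2 (MAD), the T1/2z rows show a geometric LS mean and a ratio. The Tmax rows show "Hodges-Lehmann estimate (Median)" and, for SAD and MAD Day 1, "Hodges-Lehmann CI". Every ratio row reads "Geometric mean ratio(90% CI) (female vs male)". Neither shell has a row for a p-value.

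**The concern.** Three instructions for one analysis cannot all be followed.

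- **Test.** A signed-rank test works on within-pair differences or on one sample against a fixed value. A comparison of men with women offers neither.
- **Parameter.** t1/2z is given two methods in the text. Tmax has one method in the text (MAD), another in the shells, and none in the text for SAD.
- **Direction.** The ratio is male over female in the text and female over male in the shells.

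Section 12 records the sex comparison as a deliberate addition to the planned analysis, and the final analysis follows unblinding. If the SAP stays as it is, the test, the method for each parameter and the direction will be settled at programming, with the data in hand. The direction conflict could also show the wrong sex as having the higher exposure.

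**Working it through.** The SAP gives no power, sample size or number per sex for this comparison, so there is no planned figure to reproduce. The check sets the places side by side and uses short arithmetic to show what each conflict does.

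**1. Method by parameter**

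| Parameter | 3.3, log-scale list | 3.3, non-parametric sentence | 10.7 list | Shells 14.2.8.1-2 |
|---|---|---|---|---|
| t1/2z, SAD | yes | yes | yes | geometric LS mean and ratio |
| t1/2z, MAD Days 1 and 7 | yes | yes | yes | geometric LS mean and ratio |
| Tmax, SAD | no | no | yes | Hodges-Lehmann |
| Tmax, MAD Days 1 and 7 | yes | no | yes | Hodges-Lehmann |

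For t1/2z the log-scale list and the shells agree, and the non-parametric sentence is the outlier. For MAD Tmax the text and the shells disagree. For SAD Tmax, 10.7 points to a method that 3.3 does not give.

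**2. Can a signed-rank test be run?**

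Planned active subjects: SAD 5 × 6 = 30; MAD 3 × 6 = 18. Each belongs to one sex. A participant random effect creates no pairs, because no participant is observed at both levels of sex.

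- *Unequal groups.* With an assumed split of 18 and 12, a two-sample signed-rank call fails. At most 12 arbitrary pairs could be formed, dropping 18 − 12 = 6 subjects.
- *Equal groups.* Pairs can be formed, but the p-value depends on how. This was illustrated on assumed data only: log-normal half-lives, log-means 2.3 (men) and 2.5 (women), log-SD 0.3, one data set per split, 2,000 random pairings.

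| Assumed split | Signed-rank p over pairings: minimum, median, maximum | Rank-sum p |
|---|---|---|
| 15 / 15 | 0.008, 0.083, 0.28 | 0.034 |
| 9 / 9 | 0.13, 0.65, 1.0 | 1.0 |

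In the first row the answer falls on either side of the SAP's two-sided 10% level according to the pairing. The second row does not cross 10%, so the size of the effect varies by data set.

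- *One sample.* Applied to 30 half-lives, all positive, the exact two-sided p is 2 × (1/2)^30 = 1.9 × 10⁻⁹ whatever the sexes. It tests whether half-life is centred on zero and says nothing about men versus women.

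The two-sample Hodges-Lehmann shift is the median of all female-minus-male differences. The test that corresponds to it is the Wilcoxon rank-sum (Mann-Whitney) test.

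**3. Direction of the ratio**

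female/male = 1 / (male/female). An assumed male/female ratio of 0.80 with CI 0.65 to 0.98 becomes 1 / 0.80 = 1.25 with CI 1 / 0.98 = 1.02 to 1 / 0.65 = 1.54. If the contrast is coded from the text and the shell label is kept, the table prints 0.80 where 1.25 is correct, or 1.25 where 0.80 is correct.

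**The case against.** The case for treating this lightly has weight. The sex comparison is not among the objectives or endpoints in Sections 2.2 and 2.3; it is exploratory, and 3.3 says that no formal hypothesis testing is planned. The shells have no p-value row, so the faulty p-value has no place in the planned tables. The Hodges-Lehmann sentence already implies two independent samples, so signed-rank is probably a slip for rank-sum, and with unequal groups a two-sample call would fail visibly. A ratio and its reciprocal carry the same information if the label is right. All of this stands and limits the severity. It does not make the text correct: the named test is still wrong, and text and shells still cannot both be followed.

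Three stronger readings are tempting but not supported:

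- *The whole sex analysis is invalid.* The signed-rank error does not reach the mixed-model ratios and intervals for the dose-normalized Cmax and AUC parameters, which fill most of these tables.
- *The shells simply reverse the text.* For t1/2z the log-scale list and the shells agree. For SAD, 3.3 does not put Tmax in the log-scale model at all.
- *The spread of p-values over pairings measures the error in this trial.* Group sizes, medians and variability were all assumed, random pairing is not something the SAP proposes, and the spread changes with the data set. It only illustrates why the test does not fit.

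**Conclusion.** Wrong as written, and should be fixed. Section 3.3 specifies a paired test for independent groups. It also gives t1/2z two methods, puts MAD tmax in a model where the shells use Hodges-Lehmann, leaves SAD Tmax without a method, and defines the ratio opposite to the shells. These conclusions come from reading the document and rest on no numerical assumption beyond each participant belonging to one sex.

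The effect is confined. The test error concerns one exploratory p-value per analysis day. The direction conflict could invert every reported sex ratio (1.25 against 0.80), but only if the contrast follows the text while the label follows the shell. Neither bears on the primary safety endpoints or on the dose-proportionality and food-effect analyses. That is why it does not rank as critical.

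**What to change.** 1. In 3.3, state that Tmax (SAD, MAD Day 1, MAD Day 7) is compared by the two-sample Hodges-Lehmann shift, female minus male, with a 90% CI.
2. If a p-value is wanted, name the Wilcoxon rank-sum test and add a row to both shells. Otherwise delete the p-value sentence.
3. Analyse t1/2z on the log scale only. Remove it from the non-parametric sentence and remove tmax from the log-scale lists.
4. Make the parameter lists in 3.3 and 10.7 agree, with SAD Tmax in both. Section 10.7 states no ratio direction, so nothing needs correcting there on that point.
5. Use one ratio direction in 3.3 and Tables 14.2.8.1-2. Either would do; female over male leaves the shell labels unchanged.
6. Check that the Tmax rows show one shift and its CI in all three panels. As they read now, the estimate row has a value under each sex, and the Day 7 panel shows no CI row.

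The cost is a few sentences in 3.3, a check of the 10.7 list and small edits to two shells. No new data are needed, and the change should be made before unblinding.

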3.5 Handling of Missing Data

For the classification of Treatment emergent adverse event (TEAE), Medical History and Concomitant medication, the following will be applied in the following order:

- If all dates/times (start and stop) missing, the event/medication will automatically be classified as a TEAE/Concomitant medication.
- For AEs with a missing start date/time, if the event end date/time is prior to first study drug administration, the event will not be classified as a TEAE.
- If only the AE start year/ medication end year is present and is the same or is after the first study drug administration year unit, the event/medication will be classified as a TEAE/Concomitant medication.
- If the AE start month and year/medication end month and year are present and are the same or after the first study drug administration month and year units, the event/medication will be classified as a TEAE/Concomitant medication.
- If start AEs, Concomitant Medication and Medical History Day is missing, it will be assigned as 1st Day of the Month. If AEs, Concomitant Medication and Medical History Month is missing, it will be assigned as 1st Month of the Year and if AEs, Concomitant Medication and Medical History Year is missing, Informed Consent Year will be used.
- If end AEs, Concomitant Medication and Medical History Day is missing, it will be assigned as 31st. If AEs, Concomitant Medication and Medical History Month is missing, it will be assigned as 12.

For the PK analysis the following will be applied:

- For the concentration descriptive summaries, concentrations may be excluded if sampling time deviation is considered large to affect the profile at the discretion of the pharmacokineticist.
- Concentrations that are below limit of quantification (BLQ) prior to the first quantifiable value will be set equal to zero. Post dose BLQ concentrations, post T_{\max} , will be set to missing.

- c. Where there are no results (NR), these will be set to missing.
- d. If more than 75% of values per nominal timepoint and treatment group are BLQ, then all descriptive statistics, except for nBLQ, will be denoted as not calculable (NC).
- e. For the calculation and graphical representation (semi-log and log-log plots) of geometric descriptive statistics, 0 values will be set to missing.
- f. For the purpose of calculating the non-compartmental PK parameters, concentrations that are BLQ prior to the first quantifiable value will be set equal to zero. BLQ values after measurable concentrations will be set to missing. Concentrations in the terminal phase, which is preceded by two BLQ values, will be set to zero.
- g. For the calculation of summary statistics of PK parameters, all NR and NC values in a data series will be set to missing.

Conversion of categorical values

In some instances, continuous variables are expressed as a range (i.e., < 10). In such cases, values may be converted to the range boundary (upper or lower limit as applicable). As an example, a value of <10 may be converted to 10. Such substitutions will be clearly documented in the footnotes of relevant outputs.

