11.1 Adverse Events

All AEs including will be coded using latest MedDRA version. All AE summaries will be restricted to TEAEs only. AEs will be grouped by system organ class (SOC) and preferred term (PT) and summarized, by actual treatment group and overall. Summary tables will include the number of participants (%) experiencing an event and the number of events. Participants will be counted only once for each SOC and PT level; they will be sorted alphabetically and for PT tables only, they will be ordered with the highest first (categorical descriptive analysis).

For food effect cohort, an adverse event starting in one period and continuing into the next period is counted only in the onset period.

Assigned treatment	Definition
Treatment Period 1 (Fasting)	AE start date/time is on or after the dose date/time of treatment received in Period 1 and prior to the date/time of treatment received in period 2 (fed period) no matter when AE stops.
Treatment Period 2 (Fed)	AE start date/time is on or after the dose date/time of treatment received in Period 2 until the end of study.

For Part 1 (SAD) Cohort S3 food effect arm, TEAE will be further assigned to S3/Fasted (period 1) or S3/Fed (period 2) by using period 2 start date and TEAE's that start post first study drug administration of period 2 (Fed) will not be attributed to treatment during period 1 (Fasted). TEAE's that start post first study drug administration of period 1, but prior to first study drug administration of period 2, will be attributed to period 1 only. TEAEs that start post first study drug administration of period 1 (Fasted) and ongoing will be attributed to Onset period only

The TEAE summaries will include:

- Overall summary of TEAEs.
- TEAE summary by SOC and PT.
- TEAE summary of serious events by SOC and PT.
- TEAE summary by SOC, PT and Severity.
- TEAE summary by SOC, PT and relationship to study drug.
- TEAE summary of events leading to the study drug discontinuation by SOC and PT.
- Overall Frequency of TEAE by PT.
- Overall Frequency of related TEAE by PT.

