If a participant has multiple occurrences of a concomitant medication, the participant is presented only once in the participant count (n) column for a given ATC and PT. Occurrences are counted each time in the mentions/occurrence (m) column.

Percentages are calculated (the denominator used for the calculation) based on the number of participants in the safety population in each treatment group (N).

World Health Organization-Drug Dictionary (WHO-DD) Version xx, YYYY

Programing Note:

Add following treatment columns;
 CVN766 5 mg, CVN766 15 mg, CVN766 45 mg(Fasted), CVN766 45 mg(Fed) CVN766 125 mg, CVN766 250 mg, Overall CVN766, Overall Placebo, Placebo (Fed) and Overall
 Overall CVN766 will not contain CVN766 45 mg(Fed)
 Overall Placebo will not contain Placebo (Fed) from S3 Cohort.

Table 14.3.2.2 Summary of Concomitant Medications MAD (Safety Population)

Programing Note:
Same as Table 14.3.1.1
Source: Listing 16.2.10.2.2
Add following treatment columns;
CVN766 45 mg, CVN766 125 mg, CVN766 250 mg, Overall CVN766, Overall Placebo and Overall.

Table 14.3.3.1.1 Summary of Overall Treatment Emergent Adverse Events SAD (Safety Population)

	CVN766 5 mg (N=xx) n (%) m	etc.	Overall (N=xx) n (%) m
Number of Participants Reporting at least one:			
TEAE	xx (xx.x%) xx	xx (xx.x%) xx	xx (xx.x%) xx
Severe TEAE	xx (xx.x%) xx	xx (xx.x%) xx	xx (xx.x%) xx
Treatment Related TEAE	xx (xx.x%) xx	xx (xx.x%) xx	xx (xx.x%) xx
Serious TEAE	xx (xx.x%) xx	xx (xx.x%) xx	xx (xx.x%) xx
TEAE leading to study drug withdrawal[1]	xx (xx.x%) xx	xx (xx.x%) xx	xx (xx.x%) xx
TEAE leading to discontinuation from study	xx (xx.x%) xx	xx (xx.x%) xx	xx (xx.x%) xx
Life threatening TEAE	xx (xx.x%) xx	xx (xx.x%) xx	xx (xx.x%) xx
TEAE leading to death	xx (xx.x%) xx	xx (xx.x%) xx	xx (xx.x%) xx

Source: Listing 16.2.7.1.1

Treatment Emergent Adverse Events (TEAEs) are defined as adverse events that occurred following the first administration of study medication. If a participant has multiple occurrences of a TEAE, the participant is presented only once in the Participant count (n) column for a given System Organ Class and Preferred Term. Occurrences are counted each time in the mentions/Occurrence (m) column.

Percentages are calculated (the denominator used for the calculation) based on the number of participants in the safety population in each treatment group (N).

[1]Action taken = drug withdrawn

Medical Dictionary for Regulatory Activities (MedDRA) Version xx.x

Programing Note:

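### Partial AE start dates are imputed with no floor at first dose, which leaves some AEs with an unknown start dated before dosing and moves many S3 fed-period AEs with a missing start day to Fasted

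*SAP*

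**What the plan says.** Section 3.5 lists six date rules for AEs and medications and says that "the following will be applied in the following order". Numbered as listed, for AEs:

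1. "If all dates/times (start and stop) missing, the event/medication will automatically be classified as a TEAE/Concomitant medication".
2. "For AEs with a missing start date/time, if the event end date/time is prior to first study drug administration", it is not a TEAE.
3. "If only the AE start year/ medication end year is present and is the same or is after the first study drug administration year", it is a TEAE.
4. Month and year known, and equal to or later than those of first dose: TEAE.
5. "If start AEs, Concomitant Medication and Medical History Day is missing, it will be assigned as 1st Day of the Month"; a missing month becomes January and a missing year becomes the consent year.
6. "If end AEs, Concomitant Medication and Medical History Day is missing, it will be assigned as 31st"; a missing end month becomes December.

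Rules 1 to 4 classify; rules 5 and 6 impute.

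Section 3.2 defines a TEAE as occurring within 30 days after dosing, with the formula onset − last dose + 1 ≤ 30. The footnotes of the mock TEAE tables say: "Treatment Emergent Adverse Events (TEAEs) are defined as adverse events that occurred following the first administration of study medication".

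For S3, the section 11.1 table puts an AE in Fasted if "AE start date/time is on or after the dose date/time of treatment received in Period 1" and before the Period 2 dose, and in Fed if it starts at or after the Period 2 dose. The text below the table splits S3 TEAEs by the Period 2 start date. Section 3.7 keeps S3 Fed out of Overall CVN766.

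**The concern.** Rules 1, 3 and 4 are conservative: where the date is unclear, the event counts as treatment-emergent. Rule 5 then works the other way. It takes the earliest date that fits the known part, whether or not that date precedes dosing. Two later steps depend on the start date: the S3 period assignment in section 11.1, and the TEAE status of any event that rules 1 to 4 leave open.

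The percentage of subjects with at least one TEAE is the first primary endpoint in section 2.3. It is read in columns of six active subjects, so a single event can change a reported figure visibly.

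**Working it through.** The SAP gives no figure on this point, so there is none to reproduce.

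**Inputs.** Date rules: section 3.5. Period windows: section 11.1. Six active and two placebo subjects per cohort: section 2.5. S3 return on Day 21 and follow-up on Day 42: visit list in the mock shells. Assumptions: fed dose on Day 21, first-dose date uniform over the 365 days of 2022, onset uniform within the window, only the day missing, comparison by date.

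**1. Start wholly missing, end after dosing.** Take first dose 10 June 2022, consent in 2022, AE end 12 June, no start.
- Rule 1 fails because an end date exists. Rule 2 fails because the end is not before dosing. Rules 3 and 4 fail because no part of the start is known.
- Rule 5 gives 1 January 2022. The section 3.2 formula gives −160 + 1 = −159, which is ≤ 30. But the words of section 3.2 and the table footnote both require onset after dosing, and this date fails them.
- Remove the end date as well, and rule 1 makes the same event a TEAE. Evidence that the event lasted past dosing makes it less likely to count.

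**2. S3 fed-period events, month and year known.** Example: fasted dose 15 July, fed dose 4 August (20 days later), true onset 8 August, recorded as 2022-08-NK. Rule 5 gives 1 August, which lies between the doses, so the event is counted as Fasted.

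For onsets on Days 21 to 42 the lag from the fed dose is 0 to 21 days, mean 10.5. The imputed date is at or after the fed dose only if the onset falls in a later month, or if the fed dose was on the 1st:
- later month: 12 × 10.5 / 365 = 34.5%
- fed dose on the 1st: 12 / 365 = 3.3%
- correctly Fed: 37.8%

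Enumeration over all dose dates splits the other 62.2% into 54.8% placed in Fasted and 7.4% dated before the first dose.

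| Fed dose on | To Fasted | Before first dose | Correctly Fed |
|---|---|---|---|
| Day 15 | 43.2% | 19.0% | 37.8% |
| Day 21 | 54.8% | 7.4% | 37.8% |
| Day 22 | 56.2% | 6.0% | 37.8% |

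**3. Events in the dosing month.** The 1st precedes first dose unless dosing was on the 1st: 1 − 12/365 = 96.7%. Example: fasted dose 10 June, AE 2022-06-NK. Rule 4 makes it a TEAE and rule 5 dates it 1 June, which meets neither row of the section 11.1 table. For true fasted-period onsets (lag 0 to 19, mean 9.5) the share is 1 − 12 × 9.5/365 − 12/365 = 65.5%. The sentence below the table, which uses only the Period 2 date, would put these in Fasted, which is correct for them. On that reading the 7.4% of fed events also go to Fasted, giving 54.8 + 7.4 = 62.2% misplaced.

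**4. Size of one event.** If it is the subject's only TEAE in that column: 1/6 = 16.7 points in a dose group, 1/30 = 3.3 in SAD Overall CVN766, 1/18 = 5.6 in MAD Overall CVN766.

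**5. End dates.** The 31st does not exist in five months of the year. No summary result was found that turns on this.

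**The case against.** The strongest reply is that section 3.5 is ordered. Classification comes before imputation, so an event made a TEAE by rule 1, 3 or 4 is not tested again. The section 3.2 formula has no lower bound: for a 20 June dose, imputed dates of 1 June and 1 January give −18 and −169, both ≤ 30. This stands. A reader might infer that rule 5 removes such events from the primary TEAE count, but that would happen only if a programmer re-tested the imputed date against the table footnote.

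A reader might also infer that two thirds of fasted-period events with a missing day belong to no period. That depends on the section 11.1 table alone and disappears under the sentence below it. What remains is that table and text disagree.

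Nor are imputed dates almost always pre-dose. The 96.7% applies to the dosing month, and year-only dates behave similarly. Over all onsets the share is 75.3% for SAD Days 1–14, 63.8% for MAD Days 1–21 and 35.0% for S3 Days 1–42.

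A 50-point shift for one placebo subject fits only the Placebo (Fed) column. Pooled placebo has 10 subjects in SAD and 6 in MAD.

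Finally, partial dates may be rare, since the AE listing records start date and time and subjects are in clinic around dosing. That limits the expected size but does not repair the rule.

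**Conclusion.** The point holds in a limited form. Rule 5 needs a floor at first dose, and the S3 period rule needs a provision for partial dates.

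- An AE with no start and an end at or after first dose has no stated TEAE status and receives a pre-dose date. This is the one route by which an event could leave the overall TEAE count without anyone departing from section 3.5.
- About 55% of S3 fed-period events with a missing start day go to Fasted and into Overall CVN766 (43% to 56% for a fed dose on Day 15 or Day 22). This is conditional on uniform onsets and dose dates, with month and year recorded.
- A TEAE in the dosing month carries an onset that the section 11.1 table cannot place, although the text below it can.

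The number of events affected cannot be estimated, because the frequency of partial dates is not given. One such event can still move a six-subject column by 16.7 points.

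**What to change.** In section 3.5:
- State that the classification under rules 1 to 4 is final and is not re-derived from imputed dates.
- Classify an AE with a missing start and an end on or after first dose, or ongoing, as a TEAE.
- Impute a partial start as the later of the first day of the known month or year and the first dose date/time, never after a known end date.
- Impute a missing end day as the last calendar day of the month.

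In section 11.1:
- Reconcile the period table with the sentence below it.
- Where a known end date decides the period (an end before the fed dose means Fasted), use it.
- Flag TEAEs whose partial start fits both periods, and show the S3 counts once with them in Fasted and once in Fed.

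The floor alone is not enough: it removes the pre-dose dates but leaves 62.2% of fed-period events with a missing day in Fasted. Sending every event from the fed-dose month to Fed is no better. Fasted onsets lie 1 to 20 days before the fed dose (mean 10.5), so 1 − 12 × 10.5/365 = 65.5% of those with a missing day would move to Fed and out of Overall CVN766.

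The cost is a few lines of SAP text, one derivation and a small sensitivity count, with no new data. A few ambiguous events will be attributed to treatment.
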